#### **5.4.5 BMI**

$$\text{BMI (kg/m}^2\text{)} = \text{Body weight (kg)} / \{\text{Body height (m)}\}^2$$

Round off the second decimal place and report the value to the first decimal place.

#### **5.4.6 Medical history and Adverse events**

All medical history and adverse events will be coded from the verbatim terms reported by the investigator term using the Medical Dictionary for Regulatory Activities (MedDRA) version 20.0 or the later version.

#### **5.4.7 Adverse reactions**

Adverse reactions are defined as adverse events that are determined to have a “reasonably possible” causal relationship to the study drug.

#### **5.4.8 Duration of the AE and time to the AE**

Duration of the AE and time to the AE occurrence from start of study medication will be calculated and presented in days, where AE duration = AE stop date – AE start date + 1 and the time to the AE occurrence = AE start date – first DB dose date + 1.

#### **5.4.9 Prior and Concomitant medications**

Prior and concomitant medications are medications other than Study treatment. They are derived by comparing their start and stop dates with the first treatment dose date.

Prior medications are those which stopped prior to first dose of double-blind study medication. Concomitant medications are medications that started prior to, on or after date of first dose of double-blind study medication and ended on or after date of first dose of double-blind study medication. This includes medications deemed as ongoing at the end of study.

#### **5.4.10 Study Treatment Exposure**

The duration of exposure is calculated as the total number of days that the subject has been treated with double-blind study medication— that is, from the treatment start date to the date of their EOT visit. For subjects lost to follow up, the treatment end date is taken to be the date of their last visit. Interruptions, compliance, and dose changes are not taken into account for duration of exposure.

Duration of exposure (days) = EOT visit date – first treatment distribution date +1.

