In case of permanent discontinuation from study, the end of treatment and follow-up visit assessments should be performed, as completely as possible (Sections 5.3.2.7 and 5.3.3, respectively). Unresolved AEs and SAEs will be followed up on according to Section 8.10.

For discontinued subjects who will not revisit the clinic, the site will perform scheduled phone calls for the collection and source documentation for safety information (AEs, concomitant medication, and date of last dose of medication). Return of unused medication and any other materials (e.g., diary) will be performed by courier where allowed.

In the event that a subject elects not to return to the study site for the end of treatment or Follow-up visit, the Investigator must make every effort to contact the subject to review/capture all AEs, assess dosing compliance, review concomitant medication and make every effort to complete all end of study assessments.

Subjects withdrawn from the study following randomization onto double-blind treatment may not re-enter the study. Subjects withdrawn from treatment may remain on study and continue with study procedures off treatment based on the Investigators clinical discretion.

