**Table 5 Analysis Visit Windows for the non-diary data**

Analysis visit	Nominal day	Window
Screening	Day -14	By Day -14
Day 1	First dose day	NA
Week 1	Day 8	Day 3 to 11
Week 2	Day 15	Day 12 to 22
Week 4	Day 29	Day 23 to 42
Week 8	Day 57	Day 43 to 71
Week 12	Day 85	Day 72 to 99
Week 16	Day 113	Day 100 to 134
Week 22 (FU)	Day 155	NA
End of treatment (EOT)	Week 16 study visit or study early termination visit	

The analysis visits are derived according to the following criteria:

- The unscheduled visits are not used for the deriving.
- If a study visit is the only one in an analysis visit window, this study visit becomes the derived analysis visit.
- If there are multiple visits in an analysis visit window, the closest visit to the nominal day becomes the analysis visit. In the event that two visits are the closest visits to the nominal day and equally distanced to the nominal day, the visit after the nominal day becomes the derived visit.
- The follow-up visit will not be derived. The study visit will be used.

- Unscheduled visits and retests (same visit number assigned), will not be displayed in by-visit summary tables, but will be included in the data listings.
- The deriving analysis visit is not applicable to the data not depending on study visit, for example, the AE data.

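### SAP 5.4.10 ends treatment exposure at the EOT visit, not the last dose, so subjects who stop drug but stay on study have off-drug days counted as exposure

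*SAP*

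**What the plan says.** SAP 5.4.10 introduces duration of exposure as the number of days on double-blind medication, then fixes its end: "that is, from the treatment start date to the date of their EOT visit". The formula is "Duration of exposure (days) = EOT visit date – first treatment distribution date +1". Two further rules apply:

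- Loss to follow-up: "For subjects lost to follow up, the treatment end date is taken to be the date of their last visit".
- Gaps in dosing: "Interruptions, compliance, and dose changes are not taken into account for duration of exposure".

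SAP Table 5 defines EOT as "Week 16 study visit or study early termination visit".

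Protocol 4.5 separates stopping treatment from leaving the study. On the first it says: "Subjects withdrawn from treatment may remain on study and continue with study procedures off treatment", at the investigator's discretion. It also asks that such subjects be encouraged to attend all remaining visits. On the second it says: "In case of permanent discontinuation from study, the end of treatment and follow-up visit assessments should be performed".

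Two other SAP sections bear on the point. Section 7.8 summarizes duration of exposure together with total dosed days, but section 5.4 gives no derivation for the latter. Section 5.4.11 uses duration of exposure as the denominator of compliance and subtracts missed days in the numerator.

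**The concern.** The description in SAP 5.4.10 and its formula agree only when drug stops at about the EOT visit. The protocol expressly provides for subjects for whom this is not so: off drug, still attending visits, with EOT at Week 16. No exception in 5.4.10 covers them, because the only special rule is for loss to follow-up.

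At stake is whether the exposure table shows how long each arm actually took the drug. Under the present formula, early stopping followed by continued attendance leaves no trace in duration of exposure. The same number is also the denominator for compliance, and compliance below 80% is a major deviation under SAP 2.9.

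**Working it through.** The documents give a date formula but no exposure figure, so there is no stated result to reproduce. The check applies the formula to example dates.

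**Inputs**

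- First distribution and first dose on Day 1 (Protocol 3.1 and 5.3.2.1, Visit 2).
- EOT visit at Week 16, Day 113 ± 7 (Protocol 5.3.2.7).
- Planned treatment of 16 weeks: 16 × 7 = 112 days.
- 34 subjects per arm (Protocol 4.1).
- Last dose on Day 29, 57 or 85: assumptions. The documents give no discontinuation rates or times.

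**Per subject**

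SAP duration = EOT day − 1 + 1 = EOT day. Duration to last dose = last dose day − 1 + 1 = last dose day.

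| Last dose | SAP, EOT Day 113 | To last dose | Excess | Excess, EOT Day 106 to 120 |
|---|---|---|---|---|
| Day 29 | 113 | 29 | 84 days (12 weeks) | 77 to 91 days |
| Day 57 | 113 | 57 | 56 days (8 weeks) | 49 to 63 days |
| Day 85 | 113 | 85 | 28 days (4 weeks) | 21 to 35 days |

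A completer with last dose on Day 112 and EOT on Day 113 differs by 1 day.

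**Per arm**

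Assume completers' last dose on Day 112, k stoppers with last dose on Day 57, and all subjects attending EOT on Day 113. Mean to last dose = [(34 − k) × 112 + k × 57] / 34.

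- k = 1: 3753/34 = 110.4 days
- k = 3: 3643/34 = 107.1 days
- k = 5: 3533/34 = 103.9 days
- k = 7: 3423/34 = 100.7 days

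The SAP mean is 113 days in every row. The overstatement therefore runs from 2.6 to 12.3 days over this range, about 1 day of which comes from completers.

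**Compliance for a last dose on Day 57, EOT on Day 113, no doses missed before stopping**

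- SAP 5.4.11, off-drug days counted as missed: (113 − 56)/113 = 50.4%.
- SAP 5.4.11, off-drug days not counted as missed: (113 − 0)/113 = 100%.
- Denominator shortened to the last dose: 57/57 = 100%.
- Planned-period denominator, off-drug days counted as missed: (112 − 55)/112 = 50.9%.

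The SAP does not say which of the first two applies. The third line shows that carrying a last-dose duration into 5.4.11 would class this subject as fully compliant.

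**The case against.** **EOT may fall at drug stop.** Protocol 5.3.2.7 names Visit 8 as Week 16 or early termination without saying termination of what. Protocol 3.2 puts the follow-up visit six weeks after end of treatment or early termination to look at pigmentation recovery, which fits an EOT visit held when drug stops. If sites work that way, the excess nearly vanishes. This stands as a limit on size. It does not remove the problem, because SAP Table 5 and the discontinuation paragraph of Protocol 4.5 both tie the early visit to leaving the study.

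**The SAP is open about using a calendar span, and reports a second measure.** It says that interruptions are ignored, SAP 7.8 adds total dosed days, and SAP 7.9 lists administration and accountability data by subject. This is a partial safeguard. Permanent discontinuation is not an interruption, and total dosed days has no derivation rule.

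**Consequences are easily overstated.** A reader might infer that safety rates are distorted. The documents do not support that: adverse events are summarized as subject-level counts and incidence (SAP 7.12.1), laboratory percentages use the number of subjects in the safety population (SAP 7.12.2), and no planned rate divides by exposure time. The primary repeated-measures model does not use exposure either. A reader might also infer that most affected subjects stopped for liver or nevi findings. Those are listed grounds for stopping, but no frequencies are given.

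**Using the last-dose duration everywhere would harm the per-protocol rule.** This objection stands. A subject off drug for eight weeks would rise from 50.4% (if off-drug days count as missed) to 100% compliance. That subject could then pass the below-80% rule and, if completing Week 16 in SAP 4.3 is read as attending the visit, enter the per-protocol population. Review of deviations and populations at the blinded data review meeting may catch such a case, but the rule should not depend on it.

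**Conclusion.** The point holds in a limited form. For subjects who stop drug and stay on study until Week 16, SAP 5.4.10 reports days since first distribution as days of exposure. The excess is 84, 56 or 28 days for an assumed last dose on Day 29, 57 or 85 with EOT on Day 113. Completers change by about a day.

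The effect reaches the descriptive exposure table and the compliance denominator and goes no further. In an arm of 34 with Day 57 stops, the mean is overstated by 2.6 days with one such subject and 12.3 days with seven. The true number is not in the documents, and the overstatement is small if the EOT visit is held when drug stops.

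A reader might go on to infer that the present denominator by itself distorts per-protocol membership. It does not if off-drug days count as missed. The gap there is that SAP 5.4.11 does not say whether they do. This is a correction worth making before database lock, with no bearing on the primary efficacy result.

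**What to change.** 1. **SAP 5.4.10:** set duration of exposure = last dose date − first dose date + 1. When the last dose date is missing, use the recorded date of withdrawal from treatment, or the EOT or last visit date.
2. **SAP 5.4 and 7.8:** give a derivation for total dosed days, so that interruptions before the last dose can be seen beside the calendar span.
3. **SAP 5.4.11:** do not carry the shortened duration into compliance for the per-protocol rule. Keep the planned treatment period (112 days) as denominator and state that days after permanent treatment discontinuation count as missed, so that early stoppers are not classed as compliant.

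The cost is a few lines of SAP text and the matching programming. Protocol 4.5 requires the withdrawal date to be recorded in the eCRF for anyone who discontinues treatment or study early. Protocol 6.8 records the most recent dose date with each PK sample. Protocol 4.5 names the "date of last dose of medication" only for discontinued subjects who will not return to the clinic, so its availability for those who stay on study should be confirmed. That is why the fallback is needed. Reported exposure will fall for early stoppers and by about a day for completers.

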#### 5.4.11 Study Treatment Compliance

Compliance with double-blind study medication—based on the drug accountability data—will be calculated as the number of days subjects take study medication divided by the duration of exposure in days, expressed as a percentage.

Study medication compliance will be calculated as follows:

$$\frac{\text{duration of exposure (days)} - \text{number of days subject miss the medication}}{\text{duration of exposure in days}} \times 100\%$$

The subjects should take one dose daily per protocol.

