7.3 Compliance

The prescribed dosage, timing, and mode of administration of study medication will not be changed. Subjects will be asked questions regarding the compliance, any departures from the intended regimen will be recorded in the eCRF.

Study medication accountability and subject compliance will be documented throughout the double-blind treatment period using study-specific study medication dispensing and return record forms. For subjects who do not return their [REDACTED], the site will question each to determine compliance (e.g. number of doses missed since the last visit).

Subjects will be asked to return all unused medication including empty and partially used [REDACTED]. Study medication dispensed at the previous visit will be retrieved by the Investigator and compliance assessed by returned medication count.

Non-compliance will be defined as taking $\leq 80\%$ or $\geq 120\%$ of study medication during any evaluation period (from any visit to the following visit).

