## **2.9 Protocol Deviations**

Protocol deviations will be documented, reviewed and determined in the blinded data review meeting (BDRM). Protocol deviations potentially influencing the evaluation of the primary endpoint will be defined as major deviations in order to define PP population in Section 4.3. The major protocol deviations will be selected in this meeting.

At least the following will be included as major protocol deviations:

- I/E criteria violation with significant impact on efficacy
- Overall drug compliance is less than 80% or greater than 120%
- Taking wrong treatment

The BDRM meeting minutes will serve as the main document for protocol deviations.

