## 7.9 Treatment Compliance

Compliance to Double-Blind study medication will be presented for the safety population in table by treatment.

The range 80%  $\leq$  compliance  $\leq$  120% will be used to define a subject being treatment compliant.

All study medication administration and accountability data will be listed by subject.

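### The SAP's day-based compliance formula stops at 100%, so its 120% limit can never be met, and its overall value classifies subjects differently from Protocol 7.3

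*SAP*

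**What the plan says.** **The formula.** SAP 5.4.11 states that compliance rests on drug accountability data and "will be calculated as the number of days subjects take study medication divided by the duration of exposure in days, expressed as a percentage". The displayed formula is exposure days minus missed days, over exposure days. SAP 5.4.10 counts exposure from first treatment distribution to the EOT visit, both days included.

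**How the SAP uses it.** SAP 2.9 lists three items under "At least the following will be included as major protocol deviations". One is "Overall drug compliance is less than 80% or greater than 120" per cent. The same section gives a general rule: "Protocol deviations potentially influencing the evaluation of the primary endpoint will be defined as major deviations". SAP 4.3 then limits the PP population to ITT subjects without major deviations who complete Week 16. In SAP 7.9 the range from 80% to 120%, limits included, "will be used to define a subject being treatment compliant". SAP 7.9 adds: "All study medication administration and accountability data will be listed by subject".

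**The protocol.** Protocol 7.3 has study medication retrieved and "compliance assessed by returned medication count", with questioning by the site when it is not returned. It defines non-compliance as taking 80% or less, or 120% or more, "of study medication during any evaluation period (from any visit to the following visit". Protocol 7.1.2 sets 6 blinded units per day and, when the subject forgets to bring the medication back, has the site record the days missed.

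**The concern.** There are three difficulties.

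- One listed PP criterion has an upper limit that its own formula cannot reach.
- The formula counts days, while a daily dose is 6 units. The SAP does not say whether a day with fewer or more than 6 units counts as taken. If it does, partial and excess intake do not show in the value.
- The SAP and Protocol 7.3 can classify the same subject differently. They differ in unit (days against returned medication), in period (overall against any visit-to-visit period) and in the treatment of exactly 80% and 120%.

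The period matters most near the end of treatment. The Week 16 diary value comes from Days 99-112 (SAP Table 4). A dosing gap over those 14 days is diluted in an overall figure but plain in a Visit 7 to Visit 8 figure. At stake are the compliance table and membership of the PP set used for the supportive analysis of the primary endpoint.

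**Working it through.** **Inputs.** D = exposure days (SAP 5.4.10); m = missed days, m ≥ 0 (SAP 5.4.11); limits of 80% and 120% (SAP 2.9, 7.9; Protocol 7.3); 6 units per day (Protocol 7.1.2); Visit 7 on Day 85 ± 7 and Visit 8 on Day 113 ± 7 (Protocol Table 5.1-1); Week 16 diary window Days 99-112 (SAP Table 4).

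**1. Can the SAP formula reach its own limit?** C = (D − m)/D. C > 1.20 requires m < −0.20 × D. At D = 113 that is m < −22.6, which is impossible. The maximum, at m = 0, is 100%.

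**2. Days against units.** If any day with some intake counts as taken, the SAP formula gives 100% in both of these cases:
- 4 of 6 units daily: 4/6 = 66.7% by units.
- 8 of 6 units daily: 8/6 = 133.3% by units.

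**3. Where the lower limit acts.** At D = 113, 22 missed days give 91/113 = 80.5% (criterion not triggered) and 23 give 90/113 = 79.6% (triggered). Under Protocol 7.3, in a 28-day period, 5 missed days give 23/28 = 82.1% and 6 give 22/28 = 78.6% (non-compliant).

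**4. Gap on Days 99-112, otherwise fully dosed, EOT Day 113.**
- SAP overall: (113 − 14)/113 = 99/113 = 87.6%, not triggered.
- Visit 7 (Day 85) to Visit 8 (Day 113): (28 − 14)/28 = 50.0%, non-compliant under Protocol 7.3.
- The SAP criterion would need 23 − 14 = 9 further missed days.

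**5. Does this depend on visit dates?** Take Visit 7 on Days 78-92 and Visit 8 on Days 106-120: 15 × 15 = 225 combinations.

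| Measure | Lowest | Highest |
|---|---|---|
| SAP overall | 98/112 = 87.5% | 98/106 = 92.5% |
| Period, Visit 7 to the day before Visit 8 | 7/21 = 33.3% | 21/28 = 75.0% |
| Period, day after Visit 7 through Visit 8 | 6/20 = 30.0% | 20/28 = 71.4% |

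The overall value never falls below 80%, and the period value never exceeds 80% under either day count. Over these EOT days, 9 to 14 further missed days are needed to trigger the SAP criterion.

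**6. Off drug from Day 99 until EOT.** 98/122 = 80.3% and 98/123 = 79.7%. The SAP criterion triggers only from EOT Day 123, outside the Day 113 ± 7 window.

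**The case against.** The case on the other side has real weight.

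- **Data source.** A reader might infer that accountability data play no part in the PP criterion. SAP 5.4.11 says the value is based on them. The difference is that the formula takes only missed days from them. Counting days also has some basis in Protocol 7.1.2, which has sites record missed days when medication is not brought back.
- **Undeclared change.** A reader might infer that SAP Section 8, which declares no changes to the protocol's statistical analyses, is false. That is not established. Protocol 7.3 belongs to the study treatment section and does not tie non-compliance to the PP set. Protocol Section 10 sets no compliance threshold for that set. SAP 2.9 fills in a rule that the protocol left open.
- **The Days 99-112 gap.** A reader might infer that such a subject must stay in the PP set. The SAP 2.9 list is a minimum, and its general rule covers deviations that may influence the primary endpoint, so the blinded review may class the gap as major. A subject who stopped for good before Week 16 may also fail the completion condition in SAP 4.3.
- **Excess intake.** An overdose must be recorded as an AE (Protocol 8.11), so it is open to the blinded review. An upper limit that never acts excludes nobody wrongly.
- **The remedy.** A unit count can exceed 120% only if subjects hold spare supply, and the documents do not state how much they hold.

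All of this narrows the point. None of it makes the 120% limit reachable or brings the two compliance definitions into agreement.

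**Conclusion.** The point holds, with minor weight. By arithmetic alone, the 120% limit in SAP 2.9 and 7.9 cannot be met under SAP 5.4.11. That partial and excess intake go unseen is conditional: it assumes that a day with other than 6 units counts as taken, which the SAP leaves open. The disagreement with Protocol 7.3 is real. The worked gap is 87.6% overall and 50% for the last period, and the two rules disagree on it at every permitted pair of visit dates. Exactly 80% or 120% is compliant in SAP 7.9 and non-compliant in Protocol 7.3.

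The scope is the compliance table and the supportive PP analysis. The primary analysis uses the ITT population and is unaffected. A reader might infer that the PP result would be distorted, but the documents do not show that any subject's PP status would change.

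**What to change.** 1. In SAP 5.4.11, compute compliance as units taken (dispensed minus returned) over units expected (6 per day). When medication is not returned, use the missed doses or days recorded by the site (Protocol 7.1.2 and 7.3). State one day-counting rule for visit-to-visit periods.
2. In SAP 2.9, list Visit 7 to Visit 8 compliance as an item for the blinded review of PP membership.
3. Reconcile Protocol 7.3 with SAP 2.9 and 7.9 on overall against any-period compliance, and on whether exactly 80% and 120% are compliant.
4. If the day formula is kept instead, delete the 120% limit.

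**Cost.** SAP wording before database lock, together with whatever step 3 changes in Protocol 7.3; the accountability counts and missed doses or days are already recorded. The PP set may become slightly smaller. Each exclusion is 1/34 = 2.9% of a planned arm, and the documents do not allow the number to be predicted.

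Whether the upper limit then acts depends on supply. Assuming visits on nominal days (112 dosing days from Day 1 to the day before Day 113), no spare supply caps the unit count at 100%. Seven spare days at each of the four dispensing visits would allow up to (112 + 28)/112 = 125%. Both supply levels are assumptions.
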